## 10. Assessment and management of risk

Blood tests are a safe procedure, but there can be complications, such as bruising at the site of puncture and excessive bleeding. There is also the risk of needle stick injury to the person performing the test. We will minimise the risk of complications by having a trained staff member perform the blood extraction in accordance with infection control guidelines.

Lumbar puncture will be an aseptic procedure under local anaesthetic performed by a neurologist with experience to minimise the risk of infection and to maintain comfort. Atraumatic needles will be used to reduce the incidence of headache post lumbar puncture secondary to CSF leak. Potential but rare risk of lumbar puncture (approximately 1/10,000) is bleeding and nerve damage. Measures will be taken to minimise bleeding complications by applying pressure to the lumbar puncture site after the needle is removed and by not performing lumbar punctures on those on blood thinners (including aspirin, warfarin or heparin). The use of landmarks to identify site of the lumbar puncture beforehand, as well as partly withdrawing the introducer to check if there is CSF and that needle is in the subarachnoid space will minimise the incidence of nerve injuries. Telephone contact details will be provided as part of aftercare, for either the subject or their partner to access a member of the study team if there are any possible safety concerns.

Samples will be processed according to laboratory SOPs and COSHH procedures to minimise the risk of sample mismanagement and infection risk.

## 11. Statistical considerations

### 11.1 Sample size

This is an exploratory study and all analyses are descriptive. The primary endpoint of this study will be to look at the effect of oral cladribine on peripheral immunological markers over time. However, to explore the intrathecal effect of cladribine we will assess its impact on the disappearance of OCBs from the CSF. Based on published data none of the patients with MS will be expected to lose OCBs over 2 years of the study. With a power of 80%, and an alpha of 5%, we will only need 11 subjects to show a significant result if at least 50% of subjects on cladribine become OCB negative compared to a comparator group. Allowing for a 20% dropout rate we would only need to recruit 13 subjects.

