### 7.1 Inclusion criteria

1. Patients with MS who are being treated with oral cladribine at Barts Health NHS Trust will be approached to participate in this study.
2. Patients must be willing and able to undergo lumbar punctures.
3. Patients who are OCB positive in their CSF (previous diagnostic lumbar puncture).

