## 8. Study design

Patients will be required to give consent for 15mL of peripheral venous blood (plasma and serum), urine and CSF to be collected at multiple time points over 96 weeks. These samples will be collected in addition to those collected for routine clinical monitoring. They will be informed that their decision to consent for their blood products to be used in research will have no impact on their current or future treatment, and it should not affect their decision to start, continue or discontinue their MS therapy.

Venous blood samples will be analysed by flow cytometry. B cell populations will be determined using specific markers for B cell populations including CD10, CD19, CD25, CD27, CD38 and IgD. This will allow the analysis of the number of memory B cells (CD19+/CD27+), memory B cell subsets (CD19+/CD27+/IgD-/+ and CD19+/CD27+/CD25-/+) and plasmablasts (CD19+/CD27+/CD38+) in the subject's blood samples. As controls, naive B cells CD19+/CD27 and T cells (CD19

/CD3+/CD4+/CD8+) will also be examined. Whole blood for DNA extraction will be collected and stored for deep sequencing to analyse the B and T cell repertoire using Adaptive Biotechnologies' immunoSEQ technology; these assays can identify millions of T- and B-cell receptors in a single sample. Using this technology will allow us to compare the impact of cladribine on the adaptive immune system over time and to compare it with similar data from alemtuzumab treated subjects from [name] laboratory in Munster.

CSF will be collected using an atraumatic needle. CSF will be processed for routine biochemistry and aliquots will be stored for OCBs, FLC, B cells: soluble CD19 and plasma cells: soluble CD138; inflammatory markers: urine neopterin and multiplex cytokine profile; and neurodegenerative markers: NF, GFAP, NCAM, GAP-43 and S100B levels.

Study subjects will also be examined annually, have a routine annual MRI T2 lesion load and gadolinium enhancement, and the following outcome measures assessed EDSS, 9-HPT, T25FW, MSIS-29 and other routine clinical outcome measures at 24 weekly intervals.

Historical control data from 12 post-alemtuzumab treated subjects (Barts Health) for secondary endpoints (CSF OCB & FLC) and tertiary endpoints (B and T cell repertoires) will be used as comparators.

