## 11.2 Method of analysis

Depletion and re-population kinetics of B and T cell subsets will be analysed using descriptive statistics. An interim analysis of the year 1 data is planned, and a further analysis of the whole data will be performed at the end of the study. These will be calculated as a reduction relative to baseline counts and the absolute reduction in numbers. Time to nadir and recovery will be done using best-fit modelling. Categorical data based on absolute cut-offs will be presented as proportions, e.g. for absolute lymphocyte counts this will use the WHO boundaries.

Total blood IgG and free kappa and lambda light chain levels will be normalised to albumin levels. McNemar's test will be used to compare differences in OCB status between baseline and year one CSF or year two CSF. Differences in CSF and blood biomarkers, clinical and imaging parameters between baseline and 48w and 96w will be analysed using multiple regression. A detailed SAP will be prepared and approved during the recruitment period well before data becomes available.

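### Section 11.1: recruiting 13 does not allow for 20% dropout from a required 11; it covers at most 2 losses (15.4%), and a 20% allowance needs 14.

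*Combined protocol and SAP*

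**What the plan says.** Section 11.1 (Sample size) opens with "This is an exploratory study and all analyses are descriptive". It then bases the number of patients on OCB disappearance from the CSF. It assumes that no patient would otherwise lose OCBs over the two years and that at least half would on cladribine. The error rates are given as "With a power of 80%, and an alpha of 5" per cent, and the result is "we will only need 11 subjects to show a significant result". The recruitment target follows at once: "Allowing for a 20% dropout rate we would only need to recruit 13 subjects". The synopsis (Section 4) also gives 13 participants.

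Section 11.1 does not name the test, say whether alpha is one- or two-sided, or identify the comparator. Three other places bear on this:

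- Section 11.2 (Method of analysis): "McNemar's test will be used to compare differences in OCB status between baseline and year one CSF or year two CSF".
- Section 7.1 (Inclusion criteria) restricts entry to "Patients who are OCB positive in their CSF (previous diagnostic lumbar puncture").
- Section 8 (Study design) offers as comparator "Historical control data from 12 post-alemtuzumab treated subjects".

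No section provides for replacing patients who drop out, or accepts fewer than 11.

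**The concern.** The requirement (11), the dropout rate (20%) and the recruitment target (13) stand in consecutive sentences, and any two of them contradict the third. A dropout allowance should leave the required number after the stated fraction of recruits has been lost. Here it leaves fewer.

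This is the only sample-size justification in the plan, so its steps should hold. What is at stake is limited: one patient, on a secondary endpoint. OCB status does, however, depend on repeat lumbar punctures at 48 and 96 weeks, so some missing samples should be expected. Section 11.2 also promises a detailed SAP, which could carry the error forward.

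**Working it through.** **Inputs, all from Section 11.1:** 11 required, 20% dropout, 13 recruited, 50% OCB loss on cladribine against 0%, 80% power, 5% alpha. Section 8 adds 12 historical controls.

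**1. Reproducing the 11.** Section 11.1 states no formula. The two-sided normal approximation for two equal groups, with pooled variance under the null and no continuity correction, gives the stated figure. With p1 = 0.5, p2 = 0 and mean 0.25:

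n = [1.96 × √(2 × 0.25 × 0.75) + 0.842 × √(0.5 × 0.5 + 0)]² / 0.5² = 10.51, rounded up to 11 per group.

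**2. The dropout step.**

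- Expected completers from 13: 13 × 0.8 = 10.4, which is 0.6 short of 11.
- Losses that 13 can absorb: 13 − 11 = 2, and 2/13 = 15.4%. A third loss (3/13 = 23.1%) leaves 10.
- Recruits needed for a 20% loss: 11/(1 − 0.20) = 13.75, so 14. Check: 14 × 0.8 = 11.2.

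**3. Where 13 may have come from.** Adding 20% to 11 gives 11 × 1.2 = 13.2, which becomes 13 only by rounding down. Even an unrounded 13.2 covers a loss of only 1 − 1/1.2 = 16.7% of recruits.

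**4. Chance of keeping 11 or more**, assuming each patient drops out independently with probability 20%:

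- 13 recruits: P(Binomial(13, 0.8) ≥ 11) = 0.268 + 0.179 + 0.055 = 0.50.
- 14 recruits: P(Binomial(14, 0.8) ≥ 11) = 0.250 + 0.250 + 0.154 + 0.044 = 0.70.

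**5. Power if 10 rather than 11 are evaluable**, at 50% OCB loss and two-sided 5%. The answer depends on the test, which Section 11.1 leaves open.

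| Calculation | Losses needed for significance | Power at 11 | Power at 10 |
|---|---|---|---|
| Equal-group formula from step 1 | – | 82.0% | 77.7% |
| Fisher's exact test against 0 of 12 historical controls | 4 or more | 88.7% | 82.8% |
| McNemar against baseline, uncorrected chi-square | 4 or more | 88.7% | 82.8% |
| McNemar against baseline, exact | 6 or more | 50.0% | 37.7% |

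The McNemar rows treat every patient as OCB positive at baseline, as Section 7.1 implies, so all changes go one way. With 5 losses and no gains the exact p-value is 2 × 0.5⁵ = 0.0625; with 6 it is 2 × 0.5⁶ = 0.031.

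**The case against.** The best defence of 13 starts from the unrounded requirement. Adding 20% to 10.51 gives 10.51 × 1.2 = 12.61, which rounds up to 13. On that footing the expected shortfall is only 10.51 − 10.4 = 0.11 patient, and the equal-group formula gives 79.5% power at 10.4. This may explain how 13 arose, but it does not make the sentence right. Adding 20% does not cover a loss of 20% of recruits, and dividing correctly still gives 10.51/0.8 = 13.14, above 13.

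Four other points limit the weight of the finding, and they stand:

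- Against the 12 historical controls, Fisher's exact test keeps 82.8% power at 10 evaluable patients, so the stated 80% would survive. Section 11.1 does not, however, say that its 11 refers to that comparison.
- Eleven is not a cliff. An allowance usually covers expected attrition, and even 14 recruits fall below 11 about 30% of the time under the independence assumption. With 13, the chance of keeping at least 10 is 75%.
- Section 9 keeps data collected up to withdrawal, so a patient who leaves after the 48-week sample still counts in the year-one comparison. This does not help the two-year claim in Section 11.1.
- The low exact McNemar figure is mainly a mismatch between the planned test and the sample size. It is already 50% at 11, and the uncorrected version gives 82.8% at 10. It should not be attributed to the dropout step.

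**Conclusion.** The sentence is wrong as written. Thirteen recruits do not deliver 11 evaluable patients at 20% dropout; they cover up to 2 losses, or 15.4%. The error is one patient (13 against 14), an expected shortfall of 0.6. This follows from the plan's own three numbers and needs no outside assumption. Only the 50% and 70% probabilities rest on independent dropout at exactly 20%.

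The severity is minor. The calculation concerns a secondary endpoint in a study declared exploratory, and under two-sided Fisher against the historical controls the power stays above 80% with 10 evaluable patients.

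**What to change.** Keep 13 and replace the last sentence of Section 11.1 with:

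> Recruiting 13 allows for up to 2 losses (about 15%) while keeping 11 evaluable; at 20% dropout about 10 are expected to be evaluable.

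This is true whichever test is used and stays consistent with the synopsis. It needs no power figure. If power at 10 is quoted as well, name the test, its version and the comparator, because the values in the table run from 38% to 83%.

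The cost is one sentence and a less favourable stated allowance (about 15% instead of 20%). It requires no extra patients or lumbar punctures. If the sponsor prefers to keep the 20% allowance, the target has to be 14, and the synopsis must change with it.

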## 11.2 Method of analysis

Depletion and re-population kinetics of B and T cell subsets will be analysed using descriptive statistics. An interim analysis of the year 1 data is planned, and a further analysis of the whole data will be performed at the end of the study. These will be calculated as a reduction relative to baseline counts and the absolute reduction in numbers. Time to nadir and recovery will be done using best-fit modelling. Categorical data based on absolute cut-offs will be presented as proportions, e.g. for absolute lymphocyte counts this will use the WHO boundaries.

Total blood IgG and free kappa and lambda light chain levels will be normalised to albumin levels. McNemar's test will be used to compare differences in OCB status between baseline and year one CSF or year two CSF. Differences in CSF and blood biomarkers, clinical and imaging parameters between baseline and 48w and 96w will be analysed using multiple regression. A detailed SAP will be prepared and approved during the recruitment period well before data becomes available.

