## 5.2 Preclinical data

### Intrathecal plasma cell and B cell biology

In MS both quantitative and qualitative assays are used to assess pathological intrathecal IgG production, which is an indicator of intrathecal B cell and plasma cells activity. From a diagnostic perspective qualitative assays are more sensitive being abnormal in 95-98% of patients with clinically definite MS. The Ig-Index, and other similar indices, are less sensitive only being abnormal in ~70% of people clinically-definite MS. However, these indices do provide a proxy of the intrathecal B and plasma cell activity. The downside of using IgG as a marker of activity is its long circulating peripheral half-life of IgG that results in the equilibration of levels between the blood and intrathecal compartments. The equilibration ratio is very sensitive to any disruptions in blood-brain-barrier (BBB) hence the need to adjust CSF:plasma IgG ratio with the albumin quotient, an index of BBB integrity. In comparison free immunoglobulin light chains (FLCs), both kappa and lambda, have a very short circulating half-life due to their high fractional excretion rate in the kidney and catabolism. As a result levels of FLCs between the blood and CSF don't equilibrate. Therefore, CSF FLC levels are a very good proxy of intrathecal B-cell and plasma cell activity. Therefore, any drug that reduces activity of B-cells and/or plasma cells will lower FLC levels. Unfortunately, FLCs don't differentiate between B-cells and plasma cells. We are not aware of any specific soluble CSF biomarker, apart from FACs analysis of free cells in the CSF that can reliably differentiate between B-cells and plasma cells.

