## Hypotheses

1. Oral cladribine preferentially targets memory B cells and that the repopulation of B-cells is driven initially by immature and subsequently mature B-cells, but not memory B cells.
2. In people with MS (pwMS) the administration of cladribine will reduce CSF biomarkers of both B cell and plasma cell activity (OCBs and absolute free light chain levels) and markers of CNS inflammation (CXCL-13) and neuroaxonal damage (neurofilament light chain).
3. The administration of oral cladribine to pwMS will result in changes, or rejuvenation, of immune repertoire at both a B-cell (immunoglobulin) and T-cell (T cell receptor) level.

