### 6.2 Secondary objective

1. To study the effects of oral cladribine on:
  - a. CSF OCBs and free immunoglobulin kappa and lambda light chain levels (FLC).
  - b. CSF markers of inflammation, in particular CXCL-13 and urine markers of inflammation (neopterin).
  - c. CSF markers of neuroaxonal damage, in particular free neurofilament light chains.
  - d. On the peripheral repertoire B-cells (immunoglobulin) and T-cells (T cell receptor) and plasma cells (soluble receptors).
2. To compare CSF OCB positivity and CSF light chain levels with a contemporary control group of alemtuzumab treated pwMS (historical data).

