### 6.5 Secondary endpoint

1. a. Relative change in CSF OCB pre- and post-cladribine (baseline vs 48w and 96w).
- b. Relative change in CSF cytokines and chemokines (baseline vs 48 w and 96w period), in particular CXCL-13 pre- and post-cladribine and urine neopterin levels.
- c. Relative change in CSF neurofilament light chain pre-and post-cladribine (baseline vs 48w and 96w).
- d. Relative change in blood immunoglobulin levels and T cell receptor levels (baseline vs 48 w and 96w period) pre-and post-cladribine and urine immunoglobulin levels.
2. Relative change in CSF soluble CD138 (plasma cell marker) pre- and post-cladribine (baseline vs. 48w and 96w).
3. Occurrence of CSF OCB positivity and relative change in CSF FLC post-cladribine *versus* historical data post-alemtuzumab (baseline vs. 48w and 96w).

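### Does the albumin rule for free light chains leave the CSF light chain hypothesis without an analysis on its own scale?

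*Combined protocol and SAP*

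**What the plan says.** The only rule specific to free light chains is one sentence, in section 11.2 and again in the synopsis: "Total blood IgG and free kappa and lambda light chain levels will be normalised to albumin levels". Serum albumin, CSF albumin and the albumin quotient are not distinguished.

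Other parts of the protocol bear on how to read it:

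- **Section 5.2** gives the reason for albumin adjustment in terms of IgG: "hence the need to adjust CSF:plasma IgG ratio with the albumin quotient, an index of BBB integrity". Of light chains it says "As a result levels of FLCs between the blood and CSF don't equilibrate", and then "Therefore, CSF FLC levels are a very good proxy of intrathecal B-cell and plasma cell activity".
- **Hypothesis 2** (section 5.3) lists "OCBs and absolute free light chain levels" among the CSF biomarkers expected to fall.
- **Section 6.2** includes CSF FLC in secondary objective 1a. Objective 2 is "To compare CSF OCB positivity and CSF light chain levels with a contemporary control group" treated with alemtuzumab.
- **Section 6.5** mentions OCB but not FLC in endpoint 1a. Endpoint 3 covers "relative change in CSF FLC post-cladribine" against the historical alemtuzumab data, at 48 and 96 weeks from baseline.
- **Section 11.2** also sends differences in CSF and blood biomarkers from baseline to 48 and 96 weeks to multiple regression. It promises a detailed SAP, to be approved during recruitment and before data exist.
- **Section 11.1** calls the study exploratory and its analyses descriptive.

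**The concern.** The background argues that IgG needs albumin adjustment because it equilibrates across the blood-brain barrier, that light chains do not equilibrate, and that the CSF light chain level is therefore informative as it stands. Hypothesis 2 accordingly speaks of absolute levels. The methods section then appears to normalise light chains to albumin along with IgG. Read that way, the analysis would not be on the scale of the hypothesis, and a reported change would mix the change in light chains with any change in albumin.

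The suspicion is strengthened because the objectives, the endpoints and the sampling plan in section 8 mention FLC only in connection with CSF, and no endpoint names blood FLC. If the sentence concerns blood alone, the one explicit FLC rule serves a quantity that no endpoint names, and CSF FLC has no written scale. At stake would be the before-after result for CSF FLC and its comparison with the 12 historical alemtuzumab subjects. An unstated scale could in principle be chosen once results are known.

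**Working it through.** **The plan's own figure.** The protocol gives no FLC or albumin values. Its one calculated figure is the sample size in section 11.1, which concerns loss of OCBs. With 50% against 0%, two-sided alpha 5% and power 80%, the average proportion is 0.25 and

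n = [1.96 × √(2 × 0.25 × 0.75) + 0.842 × √(0.5 × 0.5 + 0)]² / 0.5² = (1.200 + 0.421)² / 0.25 ≈ 10.5, so 11 per group.

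The stated 11 is reproduced. No FLC quantity enters it, so the present question cannot affect it.

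**The two readings side by side.**

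| | Sentence covers blood only | Sentence also covers CSF FLC |
|---|---|---|
| Hypothesis 2 (absolute levels) | No conflict | Tension |
| Section 5.2 | No conflict | FLC adjusted, though the stated reason for adjusting is given for IgG only |
| Endpoint 3, section 6.5 | Relative change of an un-normalised concentration | Relative change of a normalised value |
| Regression, section 11.2 | Takes in CSF FLC; scale not written | Takes in CSF FLC; normalised |

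Grammar favours the first column: blood stands ahead of both items, and the two share the noun at the end of the phrase. In that column the absolute level of hypothesis 2 and the relative change of endpoint 3 are compatible. The first says what is measured. The second says how its change is expressed, namely as the follow-up concentration over the baseline concentration. Analysts would arrive at that quantity without further instruction.

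**How far the scales could differ under the second reading.** Let f be the fall in absolute FLC and d the change in the albumin term. Then

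apparent change = (1 − f)/(1 + d) − 1.

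The values of d below are assumptions.

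| d | f = 0 | f = 20% |
|---|---|---|
| −30% | +43% | +14% |
| −20% | +25% | 0% |
| −10% | +11% | −11% |
| 0 | 0% | −20% |
| +10% | −9% | −27% |
| +20% | −17% | −33% |
| +30% | −23% | −38% |

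For example, f = 20% with d = +20% gives 0.8/1.2 − 1 = −33%, and with d = −20% gives 0.8/0.8 − 1 = 0. The sign reverses only if albumin falls by a larger percentage than FLC. With d = 0 the scales agree. The table is ratio arithmetic. It does not show that albumin moves in these patients, nor that either scale is unbiased.

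**Timing.** The schedule in section 9 assumes six months of recruitment, about 26 weeks. The first follow-up CSF comparison is at 48 weeks. A SAP approved during that recruitment period therefore precedes any change in CSF FLC, including the year 1 interim analysis.

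**The case for a change.** The strongest case for acting is that the fluid is ambiguous, the albumin measure is nowhere given, and no sentence commits to analysing CSF FLC on the absolute scale, although a named hypothesis uses that word. The words relative change do not settle it, since a percentage change can be taken of either scale. The later SAP is not among the documents and would start from an unclear sentence. The historical comparison needs the same scale in both groups, and clarifying words would cost little.

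The factual part of this stands: the albumin measure and the CSF FLC scale are not written down. The inference drawn from it is weaker.

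- The conflict with hypothesis 2 exists only under the less natural reading. Section 5.2 gives a reason to adjust IgG but does not say that FLC must not be adjusted.
- FLC is not treated worse than its neighbours. No scale is given for CXCL-13, neurofilament light chain or soluble CD138 either, which is consistent with leaving such detail to the SAP.
- The SAP would inherit hypothesis 2 and endpoint 3 as well as the albumin sentence.
- Absolute against albumin-adjusted CSF FLC is a fair choice. The first leaves any residual barrier effect in the result. The second brings in changes in albumin.
- Confining the albumin sentence to IgG would drop a blood FLC normalisation that may be intended, with no reason for doing so, and would still leave the albumin measure for IgG unnamed.

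**Conclusion.** The concern does not call for a change. The wording is loose, but no stated rule is shown to give a wrong result. Read as a rule for blood, it agrees with hypothesis 2 and leaves CSF FLC to endpoint 3 and the regression. The remaining gap is the kind of detail the promised SAP exists to settle.

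Under the blood-only reading, or if albumin is stable, the rule makes no difference to the CSF result. Under the other reading, an assumed albumin change of 20% either way would move a 20% fall in FLC to between 0% and −33%, with nothing in the documents to say whether such changes occur. The omission of FLC from endpoint 1a looks like a slip, since endpoint 3 names CSF FLC at the same time points.

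This conclusion rests on the SAP being approved when section 11.2 says it will be, and on FLC remaining a secondary, descriptive outcome. If CSF results were analysed with no SAP in place, the choice of scale would be open to the data and the question would deserve a second look.

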This suggests that cladribine may target both peripheral and central anti-inflammatory mechanisms including pathogenic intrathecal plasma cells. We hypothesise therefore that cladribine will be effective as a treatment for progressive MS; cladribine by targeting intrathecal plasma cells in MS will reduce intrathecal IgG and free light chain production and may result in the disappearance of intrathecal OCBs. We are therefore proposing an intensive B-cell biomarker study (CLAD-B study) to explore the effect of cladribine on peripheral and intrathecal B cells and plasma cells. As cladribine has a greater impact on peripheral B cells, in particularly memory B cells (B. Ceronie, M. Zhifeng, F. Ammoscato, H. Lock, H.J. Longhurst, G. Giovannoni, D. Baker, K. Schmierer 2017), and to look at the differential effect of cladribine on both the T & B cell repertoire.

We have recently hypothesised that all effective MS DMTs, particularly high-efficacy DMTs, work via targeting the peripheral memory B-cell population and suggested that cladribine may be preferentially working as semi-selective B-cell agent (Baker et al. 2017). We now have cross-sectional pilot data from patients treated with parenteral cladribine showing prolonged peripheral memory B-cell depletion of a similar magnitude to alemtuzumab-treated patients (Baker et al. 2017; B. Ceronie, M. Zhifeng, F. Ammoscato, H. Lock, H.J. Longhurst, G. Giovannoni, D. Baker, K. Schmierer 2017). As part of this study we propose defining in detail the changes in peripheral lymphocyte subsets in both the depletion and repopulation phases after oral cladribine. In addition, we will study the effects of oral cladribine on the peripheral blood B and T cell repertoire by studying the immunoglobulin and T-cell receptor diversity.

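### Section 11.2 normalises total blood IgG to albumin, but the only albumin correction the protocol justifies is for the CSF:plasma IgG ratio

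*Combined protocol and SAP*

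**What the plan says.** Section 11.2 (Method of analysis) gives the rule: "Total blood IgG and free kappa and lambda light chain levels will be normalised to albumin levels". The synopsis carries the same sentence. Neither place says which albumin is meant (blood or CSF), whether the word blood also covers the light chains, or what the normalisation is for.

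The reasoning about albumin is in section 5.2, under intrathecal plasma cell and B cell biology. IgG persists long enough in the circulation to equilibrate between blood and CSF, and the ratio is sensitive to barrier disruption, "hence the need to adjust CSF:plasma IgG ratio with the albumin quotient, an index of BBB integrity". FLC are treated differently because they are cleared quickly: "As a result levels of FLCs between the blood and CSF don't equilibrate".

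Three other places matter:

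- Section 5.1 predicts that cladribine "will reduce intrathecal IgG and free light chain production and may result in the disappearance of intrathecal OCBs".
- Hypothesis 2 (section 5.3) names the CSF markers of B cell and plasma cell activity as "OCBs and absolute free light chain levels".
- Secondary endpoint 1d (section 6.5) begins "Relative change in blood immunoglobulin levels and T cell receptor levels" and has no albumin term.

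**The concern.** Section 5.2 puts the albumin correction on a ratio of CSF to plasma. Section 11.2 puts it on a blood concentration. An analyst who follows 11.2 literally divides blood IgG by albumin and never computes the quantity that section 5.2 describes. Two things are at stake.

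1. The prediction in section 5.1 about intrathecal IgG production gets no quantitative IgG analysis, because the one IgG concentration named in 11.2 contains nothing measured in CSF.
2. A blood immunoglobulin result, if reported on this scale, mixes change in IgG with change in albumin.

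The same sentence also normalises FLC. The section 5.2 argument gives no reason to do so, and hypothesis 2 names absolute levels.

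**Working it through.** The plan states no figure for this point, so there is none to reproduce. The check has four parts.

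**1. What each quantity contains**

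- Section 11.2 value: blood IgG / albumin (taken here as blood albumin, which the text does not specify).
- Section 5.2 quantity: (CSF IgG / plasma IgG) / (CSF albumin / plasma albumin). The denominator is the albumin quotient.

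Only the second contains CSF IgG.

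**2. Response to a fall in intrathecal IgG**

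All inputs are assumptions for illustration; the documents give none. Blood IgG is 10 g/L, blood albumin 40 g/L, the albumin quotient 0.005, and locally produced CSF IgG 30 mg/L. Passive transfer of IgG is 0.45 times the albumin quotient. Passive CSF IgG is then 0.45 × 0.005 × 10,000 mg/L = 22.5 mg/L.

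| Fall in local IgG | CSF IgG (mg/L) | CSF:plasma ratio | Section 5.2 quantity | Blood IgG/albumin |
|---|---|---|---|---|
| 0% | 22.5 + 30 = 52.5 | 0.00525 | 0.00525/0.005 = 1.05 | 10/40 = 0.25 |
| 50% | 22.5 + 15 = 37.5 | 0.00375 | 0.75 | 0.25 |
| 100% | 22.5 + 0 = 22.5 | 0.00225 | 0.45 | 0.25 |

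The blood value stays constant because blood IgG is held constant, that is, local CSF production is taken as a negligible part of the blood pool.

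Now double the albumin quotient to 0.010 with no change in local IgG. Passive CSF IgG becomes 45 mg/L and the unadjusted ratio rises from 0.00525 to 75/10,000 = 0.0075. This is the barrier effect that section 5.2 warns about. The adjusted value becomes 0.0075/0.010 = 0.75, against 1.05 before. In this simple model, then, the adjusted value is not wholly free of the barrier either and should be read beside the albumin quotient.

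**3. Effect on a blood endpoint**

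If IgG is unchanged and albumin falls by 10%, the ratio is multiplied by 1/0.90 = 1.11. An 11% rise is reported although IgG did not move. This needs no assumption about variability.

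**4. Does normalising add noise?**

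On the log scale, approximately, CV_ratio² = CV_IgG² + CV_Alb² − 2ρ·CV_IgG·CV_Alb. The ratio is noisier than IgG alone only if ρ < CV_Alb/(2·CV_IgG). The documents give no CVs and no correlation. Assume an IgG CV of 10% and an albumin CV of 5%; break-even is then ρ = 0.05/0.20 = 0.25.

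| ρ | CV of ratio / CV of IgG |
|---|---|
| 0 | √(0.0100 + 0.0025)/0.10 = 1.12 |
| 0.3 | √(0.0125 − 0.0030)/0.10 = 0.975 |
| 0.5 | √(0.0125 − 0.0050)/0.10 = 0.87 |
| 0.8 | √(0.0125 − 0.0080)/0.10 = 0.67 |

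Over assumed CVs of 5–15% for IgG and 3–8% for albumin, break-even runs from 0.03/0.30 = 0.10 to 0.08/0.10 = 0.80. At ρ = 0 the inflation runs from 1.02 to 1.89. The direction is therefore undetermined.

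**The case against.** The strongest reply is that the plan never offers blood IgG as an intrathecal measure. Hypothesis 2 and objective 1a name OCBs and FLC. Section 6.5 lists CSF OCB, CSF FLC and other CSF markers, but no CSF IgG or IgG index. Section 5.2 suggests why: it reports indices as abnormal in about 70% of clinically definite MS, against 95–98% for qualitative assays, and it rates CSF FLC as a good proxy. OCBs are themselves bands of IgG made in the CNS, and 11.2 tests OCB status with McNemar's test. All of this stands. A reader might infer that the intrathecal IgG effect has no statistic able to respond to it, or that a listed intrathecal endpoint fails. The documents support neither; only a quantitative IgG measure is missing, and adding one is optional.

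A reader might also infer that dividing by albumin makes the blood endpoint noisier. The documents do not support that. Dilution, for example, would move IgG and albumin together, and the ratio would then dampen the variation.

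The link to endpoint 1d is also uncertain. That endpoint pairs immunoglobulin with T cell receptor levels. The matching objective concerns the peripheral repertoire, which section 8 assesses by sequencing. It may not mean total IgG.

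Finally, 11.2 promises a detailed SAP, which is not among the documents and might settle the definition. That does not remove the point. The rule as stated is not merely short of detail: it attaches the correction to a different quantity from the one the protocol justifies, in two places. If it was meant as shorthand for an IgG index, it leaves out the CSF and still needs rewriting.

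**Conclusion.** The point holds as a mis-specified rule of minor severity. The albumin correction is justified for the CSF:plasma IgG ratio and prescribed for blood IgG, with no reason given for the latter.

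- **Intrathecal IgG.** The prescribed value does not respond to local IgG production: 0.25 throughout the illustration, while the section 5.2 quantity goes from 1.05 to 0.75 to 0.45. These figures rest on assumed inputs. That the prescribed value has no CSF term does not.
- **Blood immunoglobulin.** If endpoint 1d includes total blood IgG, a 10% fall in albumin alone reads as an 11% rise. This is conditional on that reading of 1d.
- **Noise.** No claim is made in either direction.
- **FLC.** The wording of 11.2 conflicts with hypothesis 2 on scale, and section 5.2 offers no equilibration argument for an albumin correction. It is unclear whether 11.2 means blood or CSF light chains.

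The primary endpoint and the OCB-based sample size are unaffected. Section 11.1 describes the study as exploratory with descriptive analyses, which limits the consequence.

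**What to change.** Amend the sentence in 11.2 and in the synopsis, and carry the change into the SAP before data are seen.

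1. Report blood IgG as measured. Keep any albumin-normalised value as supplementary only, naming the albumin compartment and the purpose. State whether endpoint 1d includes total blood IgG. Cost: wording only.
2. If intrathecal IgG is to be quantified, replace the blood normalisation with (CSF IgG / plasma IgG) / (CSF albumin / plasma albumin) at baseline, 48 and 96 weeks, and report the albumin quotient beside it. Cost: IgG and albumin assays on at most 13 × 3 = 39 CSF–blood pairs. That is at most 39 × 2 fluids × 2 analytes = 156 results, fewer where routine biochemistry already supplies them. Section 6.5 already sets CSF comparisons at these times and the schedule banks plasma and serum, so no extra visit or procedure is needed. Confirm that blood and CSF are taken together. If this measure is not wanted, item 1 stands alone.
3. State whether the FLC in this sentence are blood or CSF, and reconcile their normalisation with section 5.2 and hypothesis 2. Reporting CSF FLC as absolute levels would do so. Cost: wording only.
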